#### 4.1.2 Relative Risks

Relative risks (RRs) will be calculated as the ratio of the incidence of the health outcome in the risk and self-comparison periods. Confidence intervals (CIs) will be calculated

Protocol/Amendment No.: 070-01

using the mid-probability exact method. Consistent with the primary and secondary objectives, RRs and CIs (along with number of events and incidence) will be calculated for the analyses shown in Table 4-1.

For health outcomes occurring in the risk period but not in the self-comparison period (or vice versa), incidence for the period with one or more events will be calculated but relative risks will not be provided. Number of events will be displayed for all prespecified HCUP categories of interest, even if no events occurred.

#### 4.1.3 Multiplicity

To take into account the very large number of comparisons being undertaken in this study, a multiplicity adjustment will be applied to help interpret the safety findings. Details of the adjustment will be provided in the study's Data Analysis Plan. Both unadjusted and multiplicity-adjusted results will be presented to the SRC for review, and included in study report tables.

#### **4.1.4 Deaths**

As described previously, deaths among any study subject will be identified for the period starting at the date of their first vaccination and ending 60 days after their last vaccination. A short narrative will be prepared by a investigators, after appropriate approvals, summarizing relevant information from medical history, the cause of death as available in the database, death certificate (as available through the National Death Index), or other sources as available. This information will then be reviewed by an independent physician (i.e., not part of the study research team) to determine the cause of death. A tabulation of information pertaining to the cause of death and timing of death with respect to vaccination with GARDASIL will be provided to the SRC. The SRC will review this information to determine if there is a potential safety association with GARDASIL. No formal comparison will be made because of the anticipated small number of deaths.

Given the lag time of up to two years in the state and national death registries, a complete accounting of deaths may require a supplemental report after the study end, to be delivered after the final study report.

#### 4.1.5 Sample Size and Power Calculations

Table 4-2 outlines the approximate power to detect increases in risks for health outcomes with a two-sided  $\alpha$ =0.05 for a range of background incidence rates from 1 per 2,000 to 1 per 20,000. For a sample size of 132,000 males (or 44,000 males receiving 3 doses), the study will have 50% and 92% power to detect a relative risk of 2 and 3, respectively, for medical events with a known background incidence of 1 per 12,000 doses.

Table 4-1
Summary of Analyses to be Conducted for Study of Safety of GARDASIL in Males

			Risk Period Length	
Cohort	Comparator	Doses	(after each dose)	Report*
Regimen	Self-	All doses	Days 1-60	All interim
Initiator	comparison	combined	Days 1-14	annual reports
11111111101	Companison	Combined	Day 0	with more than
			Day 0	22,000 regimen
			Sub analyziz zaroznina	initiators
			Sub-analysis screening	accrued.
			out chronic pre-existing conditions (among	acciueu.
			HCUP codes with	Einal ranart
				Final report
			elevated relative risks):	
			Days 1-60	
D i	0-16	D 1	Days 1-14	A 11 :4i
Regimen	Self-	Dose 1	Days 1-60	All interim
Initiator	comparison		Days 1-14	annual reports
			Day 0	with more than
				22,000 regimen
			Sub-analysis screening	initiators
			out chronic pre-existing	accrued.
			conditions (among	F:14
			HCUP codes with	Final report
			elevated relative risks):	
			Days 1-60	
D .	0.10	D 1	Days 1-14	D: 1
Regimen	Self-	Dose 1,	Days 1-60	Final report
Completers	comparison	2, 3 (each	Day 1-14	
	5 1	separate)	7 1100	
Autoimmune	Background	All doses	Days 1-180	All interim
Cohort	cohort not	combined		annual reports
	vaccinated			with more than
	with			22,000 regimen
	GARDASIL			initiators
				accrued.
* Prior to accru	1 622 000		htive analyses will be provide	Final report

\* Prior to accrual of 22,000 study subjects, descriptive analyses will be provided in Interim Annual Reports.

32

Protocol/Amendment No.: 070-01

Table 4-2
Estimation of Statistical Power to Detect an Increased Risk of Medical Events in 132,000
Doses\*

	Relative Risk			
Background Incidence per Dose**	2	3	4	5
1/2,000	100	100	100	100
1/5,000	90	100	100	100
1/10,000	60	97	100	100
1/12,000	50	92	99	100
1/15,000	38	81	96	99
1/20,000	31	72	92	98

\* PASS 2008 Poisson Regression routine used; Relative Risks based on a 180 day window

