#### 3.6 STUDY ENDPOINTS

#### 3.6.1 General Safety Endpoints and Risk Periods

The general safety endpoints for the Regimen Initiator and/or Completer cohorts are all health outcomes resulting in an emergency room visit or hospitalization in each of the three following time periods of interest, referred to as "risk periods":

- 1) on the date of vaccination (i.e., Day 0; Note that Day 0 health outcomes are limited to pre-specified conditions, as further described below);
- 2) on Days 1-14 after vaccination (starting at the first day after vaccination); and
- 3) on Days 1-60 after vaccination (starting at the first day after vaccination). An example of the Day 1-60 risk periods is shown in Figure 3-2.

[figure not shown]
All health outcomes resulting in an emergency room visit or hospitalization will be evaluated, including venous embolism and thrombosis. This study will assess the incidence of the health outcome as defined by the first occurrence of the health outcome in the risk period of interest for a given subject. As a result, recurrences of health outcomes in the emergency room or hospital setting with the same diagnosis within this risk period will not be addressed (see Section 4.1.1 for further details). Also, if a subject receives his next dose of GARDASILTM prior to the end of a risk period associated with a previous dose, the risk period associated with the previous dose will be truncated on the day prior to receipt of the next dose, to avoid overlapping risk periods.

Health outcome codes reported for an emergency room visit or a hospitalization during the risk (and self-comparison) periods will be identified using claims associated with the appropriate ICD-9 diagnosis codes. Within the claims database, site of medical care encounters may be identified by a combination of corresponding procedure codes and codes for site of care. For hospitalizations, claims associated with the health outcomes will be identified between the beginning and end dates of a hospitalization. ICD-9 codes associated with an emergency room encounter will also be evaluated.

Figure 3-2

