#### 4.2 AUTOIMMUNE STUDY POPULATION ANALYSIS

The risk period for the autoimmune population begins the day after a GARDASILTM dose and ends 180 days thereafter (Table 4-1). If more than one dose is administered to an individual in the autoimmune population during the time of accrual of the general safety cohort, the risk period associated with each dose will be evaluated for the autoimmune conditions. If there is less than 6 months between these doses, the risk period associated with a dose will be truncated at the subsequent dose. For calculation of person-time, the overlapped period will be counted only once.

The approach for comparing new-onset autoimmune conditions in the risk periods following vaccination to a non-vaccinated age-matched cohort will be detailed in the study's Data Analysis Plan.

In addition to evaluating rates of new-onset autoimmune conditions in the background comparison cohort, spatial/temporal techniques to assess the existence of clusters, analyses with a self-comparison cohort, or other analyses may be requested by the Safety Review Committee if an imbalance (which will be independently defined by the Safety Review Committee) is noted among the study groups for any of the pre-specified autoimmune events, even if not statistically significant.

\*\* Background risk within a 2 month window

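### Table 4-2's power is labelled 132,000 doses but was computed on 396,000 two-month units with cut-off rates, and the study-level power sentence does not hold for the dose-by-dose Completers analyses

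*Protocol*

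**What the plan says.** The Protocol's Section 4.1.5 gives power "for a range of background incidence rates from 1 per 2,000 to 1 per 20,000". Its headline is "For a sample size of 132,000 males (or 44,000 males receiving 3 doses), the study will have 50% and 92% power" to detect RR 2 and RR 3, "for medical events with a known background incidence of 1 per 12,000 doses". The title of Table 4-2 uses another unit: "Estimation of Statistical Power to Detect an Increased Risk of Medical Events in 132,000" doses. The table's two footnotes read "PASS 2008 Poisson Regression routine used; Relative Risks based on a 180 day window" and "Background risk within a 2 month window".

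The design elements that bear on this are elsewhere in the Protocol:
- Section 3.6.1 sets the longest general safety risk period: "on Days 1-60 after vaccination (starting at the first day after vaccination").
- Section 3.7.1 allows up to three self-comparison periods of up to 60 days each and leaves the details to the data analysis plan.
- Section 3.5 stops accrual at the earliest of 135,000 Initiators, 44,000 Completers or six years.
- Section 4.1.2 names the mid-probability exact method for confidence intervals.
- Table 4-1 plans an all-doses-combined analysis and a dose 1 analysis for Initiators. For Completers it plans only dose 1, dose 2 and dose 3, each separately.

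**The concern.** Three things do not fit together. The footnotes pair a 180-day window with a background risk per two months, which suggests that each of the 132,000 units was credited with three two-month periods. The design gives 60 risk days and nominally 60 comparison days per dose. The text counts males where the table counts doses, and the two are equal only in a first-dose analysis. And 44,000 males times three doses is 132,000 only if doses are pooled, which Table 4-1 does not do for Completers.

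The power sentence speaks for the study as a whole. Section 3.3 has the Safety Review Committee weigh statistical strength when it judges possible signals. A null result for one dose in the Completers would be read against a power figure that belongs to a different and larger analysis.

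**Working it through.** **Step 1: reproduce Table 4-2.** Inputs from the Protocol are two-sided alpha 0.05, 132,000 units, a 180-day window and a two-month rate unit. 180 days is three two-month units, so N·T = 132,000 × 3 = 396,000. Assumed, because not printed: an exposed share of 0.5, and the usual Poisson-regression power formula for a binary exposure as the routine used:

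power = Φ{[√(N·T·rate) · ln(RR) − 1.96·√(1/(0.5×0.5))] / √(1/0.5 + 1/(0.5·RR))}

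At 1/12,000 with the rate entered as 0.00008, √(396,000 × 0.00008) = 5.628.
- RR 2: (5.628 × 0.6931 − 3.92)/1.732 = −0.011, power 49.6% (printed 50).
- RR 3: (5.628 × 1.0986 − 3.92)/1.633 = 1.386, power 91.7% (printed 92).

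The fit over all 24 cells:

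| Two-month units | Rates | Cells matching to the percent | Largest gap (points) |
|---|---|---|---|
| 396,000 | cut to five decimals | 24 | 0.5 |
| 396,000 | exact | 18 | 4.5 |
| 264,000 | exact | 6 | 20 |
| 132,000 | exact | 4 | 51 |

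Exposed shares of 1/3, 1/4 and 2/3 fit worse. The cut rates show in the 1/15,000 row. With 0.00006 the formula gives 37.7/81.0 for RR 2/3 (printed 38/81); with the exact rate it gives 41.8/85.5. That row therefore does not match its own label.

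**Step 2: the pooled Initiators analysis under the planned method.** Take 132,000 risk windows against 132,000 comparison windows. Events are Poisson with means 132,000·r·RR and 132,000·r (at 1/12,000: 22 or 33 against 11). Given the total, the risk-period count is binomial with probability 0.5 under no effect. Reject when a mid-P tail, P(beyond x) + ½P(x), is at most 0.025. Power is summed over all outcomes.

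| Background | RR 2 mid-P (printed) | RR 3 mid-P (printed) |
|---|---|---|
| 1/5,000 | 84.9 (90) | 100 (100) |
| 1/12,000 | 47.4 (50) | 92.7 (92) |
| 1/15,000 | 38.8 (38) | 85.7 (81) |
| 1/20,000 | 30.4 (31) | 73.7 (72) |

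**Step 3: one Completers dose, 44,000 doses at the accrual target.** The pairing of risk and comparison time is not fixed in the Protocol, so two cases are shown. With 60 comparison days per subject it is 44,000 against 44,000 windows. With 180 days it is 44,000 against 132,000. At 1/12,000 the expected risk-period events are 7.3 (RR 2) or 11 (RR 3), against 3.7 or 11 comparison events respectively in the two cases.

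| Background | 60 comparison days, RR 2/RR 3 | 180 comparison days, RR 2/RR 3 | Printed |
|---|---|---|---|
| 1/5,000 | 38.8/85.7 | 57.5/96.3 | 90/100 |
| 1/12,000 | 17.5/48.0 | 28.0/67.8 | 50/92 |
| 1/20,000 | 10.0/28.4 | 18.9/47.9 | 31/72 |

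All figures assume full follow-up, no truncated periods and no multiplicity adjustment.

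**The case against.** The strongest reply is that the headline serves the primary analysis well enough. Completers are a subset of Initiators. Stopping at 44,000 Completers therefore guarantees at least 44,000 × 3 = 132,000 doses in the all-doses Initiators analysis, and stopping at 135,000 Initiators guarantees at least 135,000. This stands: 132,000 doses is a valid floor at either accrual target, and only the six-year stop can fall below it. A reader might infer that the 44,000 × 3 figure fits no planned analysis. It fits that one.

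A reader might also infer that pooled power is really 35%/77% at 1/12,000, which the Step 1 formula gives at 264,000 units. The Protocol does not support that. The formula is pessimistic here and is not the planned method; Step 2 differs from the printed headline by under three points.

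Nor can it be said that every dose-specific analysis loses half its power. Initiators dose 1 can reach 135,000 first doses, and for common events the Completers keep good power (78%/99.8% at 1/2,000 with 60 comparison days). And 17.5%/48% is not an upper bound, since 180 comparison days raise it to 28%/68%.

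Finally, the study tests no formal hypotheses, the Protocol calls the power approximate, and every RR carries a confidence interval. This limits the consequence. It does not make the printed inputs right, nor tell the reader which analysis the sentence covers. Section 3.10.1 promises interim Completers results by an approach analogous to that for Initiators, but Table 4-1 lists no pooled Completers analysis.

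**Conclusion.** The point holds in a limited form. Table 4-2's inputs are not the design's: each of 132,000 units is credited with 180 days, and two of the six rates are cut. This rests on the footnotes and a fit of all 24 cells; the 396,000, the 1:1 split and the five-decimal rates are inferred. The text and the table also disagree on males and doses.

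For the pooled Initiators analysis the numerical effect is small, at most about five points, provided comparison time equals risk time. For each separate Completers dose the stated 50%/92% does not apply. At 44,000 doses and 1/12,000 the planned method gives between 17.5%/48% and 28%/68%, depending on how comparison time is paired. This should be corrected, but it does not undermine the primary analysis.

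**What to change.** Recompute Table 4-2 with unrounded rates, the mid-P method of Section 4.1.2 and the design's risk and comparison person-time. In Section 4.1.5 replace males with doses and state that the 132,000-dose figure refers to the all-doses-combined Initiators analysis. Add the power for each separate Completers dose at 44,000 doses, with the assumed comparison time stated next to it.

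The cost is one table and a few sentences. Some stated figures become less favourable. Accrual targets, endpoints and conduct do not change.

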#### 4.2 AUTOIMMUNE STUDY POPULATION ANALYSIS

The risk period for the autoimmune population begins the day after a GARDASILTM dose and ends 180 days thereafter (Table 4-1). If more than one dose is administered to an individual in the autoimmune population during the time of accrual of the general safety cohort, the risk period associated with each dose will be evaluated for the autoimmune conditions. If there is less than 6 months between these doses, the risk period associated with a dose will be truncated at the subsequent dose. For calculation of person-time, the overlapped period will be counted only once.

The approach for comparing new-onset autoimmune conditions in the risk periods following vaccination to a non-vaccinated age-matched cohort will be detailed in the study's Data Analysis Plan.

In addition to evaluating rates of new-onset autoimmune conditions in the background comparison cohort, spatial/temporal techniques to assess the existence of clusters, analyses with a self-comparison cohort, or other analyses may be requested by the Safety Review Committee if an imbalance (which will be independently defined by the Safety Review Committee) is noted among the study groups for any of the pre-specified autoimmune events, even if not statistically significant.

\*\* Background risk within a 2 month window

## 5.1.2 Confidentiality of Subject/Patient Records

#### For All Studies

By signing this protocol, the investigator agrees that the SPONSOR (or SPONSOR representative), Institutional Review Board/Independent Ethics Committee (IRB/IEC), or Regulatory Agency representatives may consult and/or copy study documents in order to verify worksheet/case report form data. If study documents will be photocopied during the process of verifying worksheet/case report form information, the subject/patient will be identified by unique code only; all identifying information will be masked prior to transmission to the SPONSOR.

#### For Studies Conducted in the U.S.

By signing this protocol, the investigator agrees to treat all patient data used and disclosed in connection with this study in accordance with all applicable privacy laws, rules and regulations, including all applicable provisions of the Health Insurance Portability and Accountability Act and its implementing regulations, as amended from time to time. ("HIPAA").

#### **5.1.3** Confidentiality of Investigator Information

#### For All Studies

By signing this protocol, the investigator recognizes that certain personal identifying information with respect to the investigator, and all subinvestigators and study site

Protocol/Amendment No.: 070-01

personnel, may be used and disclosed for study management purposes, as part of a regulatory submissions, and as required by law. This information may include:

- name, address, telephone number, and email address;
- hospital or clinic address and telephone number;
- curriculum vitae or other summary of qualifications and credentials; and
- other professional documentation.

Consistent with the purposes described above, this information may be transmitted to the SPONSOR, and subsidiaries, affiliates and agents of the SPONSOR, in your country and other countries, including countries that do not have laws protecting such information. Additionally, the investigator's name and business contact information may be included when reporting certain serious adverse events to regulatory agencies or to other investigators. By signing this protocol, the investigator expressly consents to these uses and disclosures.

#### For Multicenter Studies

In order to facilitate contact between investigators, the SPONSOR may share an investigator's name and contact information with other participating investigators upon request.

#### 5.2 COMPLIANCE WITH LAW, AUDIT, AND DEBARMENT

By signing this protocol, the investigator agrees to conduct the study in an efficient and diligent manner and in conformance with this protocol; generally accepted standards of Good Clinical Practice; and all applicable federal, state, and local laws, rules and regulations relating to the conduct of the clinical study.

The investigator also agrees to allow monitoring, audits, Institutional Review Board/Independent Ethics Committee review, and regulatory agency inspection of study-related documents and procedures and provide for direct access to all study-related source data and documents.

The investigator agrees not to seek reimbursement from subjects/patients, their insurance providers, or from government programs for procedures included as part of the study reimbursed to the investigator by the SPONSOR.

The Investigator shall prepare and maintain complete and accurate study documentation in compliance with Good Clinical Practice standards and applicable federal, state, and local laws, rules and regulations; and, for each subject/patient participating in the study, provide all data, and upon completion or termination of the clinical study submit any other reports to the SPONSOR as required by this protocol or as otherwise required pursuant to any agreement with the SPONSOR.

Study documentation will be promptly and fully disclosed to the SPONSOR by the investigator upon request and also shall be made available at the investigator's site upon request for inspection, copying, review, and audit at reasonable times by representatives

Protocol/Amendment No.: 070-01

of the SPONSOR or any regulatory agencies. The investigator agrees to promptly take any reasonable steps that are requested by the SPONSOR as a result of an audit to cure deficiencies in the study documentation and worksheets/case report forms.

International Conference of Harmonization Good Clinical Practice guidelines (Section 4.3.3) recommend that the investigator inform the subject's primary physician about the subject's participation in the study if the subject has a primary physician and if the subject agrees to the primary physician being informed.

According to European legislation, a SPONSOR must designate a principal or coordinating investigator (CI) to review the report (summarizing the study results) and confirm that to the best of his/her knowledge the report accurately describes conduct and results of the study. The SPONSOR may consider one or more factors in the selection of the individual to serve as the CI (e.g., thorough understanding of clinical trial methods, appropriate enrollment of subject/patient cohort, timely achievement of study milestones, availability of the CI during the anticipated review process).

The investigator will promptly inform the SPONSOR of any regulatory agency inspection conducted for this study.

Persons debarred from conducting or working on clinical studies by any court or regulatory agency will not be allowed to conduct or work on this SPONSOR's studies. The investigator will immediately disclose in writing to the SPONSOR if any person who is involved in conducting the study is debarred, or if any proceeding for debarment is pending or, to the best of the investigator's knowledge, threatened.

In the event the SPONSOR prematurely terminates a particular trial site, the SPONSOR will promptly notify that site's IRB/IEC.

#### 5.3 QUALITY CONTROL AND QUALITY ASSURANCE

By signing this protocol, the SPONSOR agrees to be responsible for implementing and maintaining quality control and quality assurance systems with written SOPs to ensure that studies are conducted and data are generated, documented, and reported in compliance with the protocol, accepted standards of Good Clinical Practice, and all applicable federal, state, and local laws, rules and regulations relating to the conduct of the study.

Protocol/Amendment No.: 070-01

36

